- Physical and neurological examination (assessment of vital signs, body biometrics and collection of adverse events and concomitant medication at all face to face visits (V1B, V3B, V4B, V6B, V7B, V9B, V10B, V12B, V13B, V15B, V16B, V17B, V18B, V20B, V21B and V22B, if applicable; electrocardiogram only in three visits: V16B, V21B and V22B).
- Blood collection for safety control and measurement of biological activity at visits: V1B, V3B, V6B, V9B, V12B, V15B, V16B, V17B, V20B, V21B and V22B.
- A MRI at visits V9B, V16B, V17B, V21B and V22B.
 - A MRI will be performed before first vaccination of Part B only if the previous MRI was performed more than 6 months (± 15 days) before V1B

Patients will undergo an amyloid-PET scan at V21B for the assessment of amyloid burden. The patients will receive lumbar puncture for CSF analysis at V21B for the assessment of changes in CSF biomarkers.

Study Population:

Patients with amnestic Mild Cognitive Impairment (a-MCI) or very mild Alzheimer's Disease (vm-AD).

Number of Subjects Planned:

To ensure the primary safety and efficacy endpoints of the study a minimum of 60 subjects with a-MCI or vm-AD per treatment group (verum and placebo) are required. The amyloid-PET positive and amyloid-PET negative patients will be independently randomized following a ratio 1:1 between verum and placebo (Part A). Thus, the study contains two treatment groups.

To ensure the primary efficacy endpoint with a potency of 85%, at least 15 subjects per treatment group (verum and placebo; 30 in total) are required to complete the study. Since a total of 120 subjects will be initially included in the study and we estimate ~40% dropouts along the clinical trial, 70 are expected to complete the Part A of the protocol.

The patients' recruitment will be competitive until the required number of patients is completed. Approximately 22 international centres will be involved: Spain (17 sites), France (3 sites), Sweden (1 site) and Italy (1 site).

Diagnosis and Main Criteria for Inclusion:

The study population will consist of patients of both sexes with a-MCI or VM-AD, who meet all the selection criteria and give their informed consent to collaborate in the study, after being informed. The inclusion of each participant will be controlled by the principal investigator of each center.

Inclusion Criteria:

A subject must meet all the following inclusion criteria:

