 - o Levels of antibody secreting cells and cytokine-secreting cells (including IFN- γ , TNF- α and IL-13)
- Assessment of disease biomarkers:
 - o Levels of A β peptides in plasma
 - o Cortical fibrillary amyloid deposition assessed by PET scans.
 - o Levels of CSF biomarkers (A β 42, Tau, P-tau, neurofilament light and neurogranin) and other A β peptide species
 - o Brain volumetric and atrophy of the hippocampus using magnetic resonance imaging
- Assessment of cognition and quality of life:
 - o Mini Mental State Examination (MMSE)
 - o Clinical Dementia Rating scale (CDR)
 - o Repeatable Battery for the Assessment of Neuropsychological Status (RBANS)
 - o Alzheimer's Disease Cooperative Study – Activities of Daily Living, Mild Cognitive Impairment (ADCS-ADL MCI)

- Columbia Suicide Severity Rating Scale (C-SSRS)
- Trail Making Test (TMT)
- Investigator Global Evaluation (IGE)
- Euroqol 5 Dimensions (EQ-5D-5L)

Part B:

Exploratory Safety Variables:

- Rate (%) of AEs
- Withdrawal criteria (continuation decision)
- Number of withdrawn patients due to AEs; cause of withdrawal
- SAEs
- Physical and neurological examination
- Concomitant medication
- Vital signs (blood pressure, heart rate, respiratory rate, body temperature), body mass (weight, height).
- Brain MRI
- EKG
- Analytical haematology, toxicology (reactive protein), biochemistry, coagulation, serology and urine test strip results

Exploratory Efficacy Variables:

- Maximal increment of specific anti-A β 40 antibody signal (antibody titers estimated by ELISA (signal OD values) in each patient with regard to the pre-treatment visit (either V0/V1 [Booster group] or V1B [Delayed start group])).
- Characterization of the immune response:
 - Level of anti-A β 40 antibodies in CSF
 - Levels of antibody secreting cells
- Assessment of disease biomarkers:
 - Levels of A β peptides in plasma
 - Cortical fibrillary amyloid deposition assessed by PET scans.
 - Levels of CSF biomarkers (A β 42, Tau, P-tau, neurofilament light and neurogranin) and other A β peptide species
 - Brain volumetric and atrophy of the hippocampus using magnetic resonance imaging
- Assessment of cognition and quality of life:
 - MMSE
 - CDR scale
 - RBANS
 - ADCS-ADL MCI
 - C-SSRS
 - TMT
 - IGE
 - EQ-5D-5L

Study Assessments and Procedures:

Medical Evaluation:

To be performed at all visits, except telephone interviews. Consists on the following tests:

- Physical and neurological examination
- Vital Signs

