4.9.2 Part B

Before any assessment or intervention for the study is completed, the investigator will inform the patient and caregiver, about the Part B of the trial. Both will receive a written detailed description of all activities and requirements involved of the Part B (Patient's Information and caregiver Leaflet), and the investigator will ensure that they completely understand the clinical trial.

Once understood and accepted, they will proceed to sign the informed consent. This will take place between Last Visit of Part A and First Visit of Part B (V1B).

The V1B should take place when the results of the last MRI test performed (either at V21 or V25 or within 6 months (± 15 days) of V1B) are available and support the vaccination.

The Part B consist in two different types of visits: vaccination visits (V1B, V4B, V7B, V10B, V13B and V18B) and safety visits (phone interview: V2B, V5B, V8B, V11B, V14B, V19B and face-to-face visits: V3B, V6B, V9B, V12B, V15B, V16B, V17B, V20B, V21B and V22B).

Data to be recorded in the eCRF (and corresponding source documents), at the Vaccination Visits (V1B, V4B, V7B, V10B, V13B and V18B):

- Medical Evaluation
 - o Physical and neurological examination (except at V1B)
 - o Vital signs (blood pressure, heart rate, respiratory rate, body temperature) before and after the Vaccination
 - o Corporal biometry (weight)
- Medical History:
 - o Record relevant past and concomitant diseases
 - o Record concomitant medication.
 - o Record any adverse events.
- Treatment:
 - o Administer the study treatment
 - o Assess vaccine reaction, local and systemic.
 - o 2 hour after vaccination vital signs and a thorough examination of the patient to assess any reaction to the vaccine will be carried out and any adverse events (AEs) recorded.
- Laboratory tests (hemogram, biochemistry and biological; at V1B: only biological)
- COVID-19 related information

Data to be recorded in the eCRF (and corresponding source documents) at the safety phone interview (V2B, V5B, V8B, V11B, V14B and V19B):

- Medical History:
 - o Local or systemic reactions to the vaccine
 - o Concomitant Medication
 - o Adverse events

Data to be recorded in the eCRF (and corresponding source documents) at the safety face-to-face visits [V3B, V6B, V9B, V12B, V15B, V16B, V17B, V20B, V21B and V22B]:

- Medical History:
 - o Local or systemic reactions to the vaccine
 - o Adverse Events, Assess vaccine reaction
 - o Concomitant Medication information update

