8.2.2 Clinical Laboratory Evaluations

Blood tests for hematology, toxicology (reactive protein), biochemistry and coagulation will be carried out at visits V0, V1, V3, V6, V9, V12, V15, V16, V17, V20, V21, V23 and V25 [Part A] and at visits V3B, V6B, V9B, V12B, V15B, V16B, V17B, V20B, V21B and V22B [Part B] or at the time of an early discontinuation (PDV) (see Table 3 and Table 5). Serology, analysis of rheumatology factors and anti-nuclear antibodies will be carried at V0 and V25. Urine test strip will be performed at visits V0, V1, V3, V6, V9, V12, V15, V16, V17, V20, V21, V23 and V25 [Part A] and at visits V3B, V6B, V9B, V12B, V15B, V16B, V17B, V20B, V21B and V22B [Part B] or at the time of an early discontinuation (PDV). Additionally, at baseline visit (V1) the ApoE genotyping. All these clinical laboratory analysis will be centralized at [REDACTED] and at Araclon-Grifols. For detailed information on clinical laboratory tests see the Laboratory Manual.

Analytical and urine test strip results will be registered in the eCRF. Data will be either entered in the eCRF (and corresponding source documents) by site staff or uploaded from electronical records afterwards to the corresponding section of the subject's eCRF as detailed in laboratory manual and data management guidelines.

The investigator must review the results of laboratory analyses when received, and sign and date them. The Investigator will be required to classify laboratory results out of the normal range reported by the laboratory as clinically significant or not according to his/her criteria. Laboratory results out of the normal range judged by the Investigator as clinically significant will be flagged and recorded in the subject's eCRF as an AE.

All patients with clinically significant abnormal laboratory values should be regularly monitored until these values return to the normal range or until another valid reason other than an adverse event related to the drug is identified.

The results of these clinical laboratory analysis carried out at the screening visit (V0), will determine the inclusion of the patient into the clinical trial. The Medical Advisor's approval is needed in V0, V16 and V16B in order to accept the continuation of the patient in the study.

At Screening Visit (V0), V21, V25 and V21B the presence of several auto-antibodies will be determined within assessment of eligibility and safety.

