8.2.4 Physical and Neurological Examinations

A complete physical examination of patients will be carried out at all face to face visits (V0, V1, V3, V4, V6, V7, V9, V10, V12, V13, V15, V16, V17, V18, V20, V21, V23 and V25 [Part A] and V1B, V3B, V4B, V6B, V7B, V9B, V10B, V12B, V13B, V15B, V16B, V17B, V18B, V20B, V21B and V22B [Part B]; and PDV, if applicable). The general patient status will be assessed including examination of neck (including thyroid), eyes, ears, throat, abdomen, skin/mucous membranes, and cardiovascular, respiratory, genito-urinary and musculoskeletal systems.

At each visit, a conventional neurological examination will be carried out, consisting in a brief inspection of cortical functions, cranial nerves, motor function, reflexes, sensory function, gait and posture. A medically certified individual will conduct the physical and neurological examination at all of the face-to-face visits. Results will be recorded in the physical and neurological examination sections of the subject's eCRF.

After the baseline visit (V1), any new finding or worsening of a previous finding from physical and neurological examination will be recorded in the subject's eCRF as an AE.

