4.1.2 Secondary Safety Variables

- Withdrawal criteria (study continuation decision)
- Physical examination:

Complete physical examinations will be performed at all face-to-face visits. These assessments include examination of the neck (including thyroid), eyes, ears, throat, abdomen, skin/mucous membranes, and cardiovascular, respiratory, genito-urinary, and musculoskeletal systems.

- Neurological examination:
Neurological examinations are performed at all face-to-face visits. These assessments include cortical function, cranial nerves, motor function, reflexes, sensory function, gait, and posture.

- Concomitant medication
Each medication will be coded to Anatomical Therapeutic Chemical (ATC) classification codes using the World Health Organization Drug classification Dictionary (WHO-DD), version WhoDrug B2 2017Q3 and defined as either a prior or concomitant medication, depending on the start and end dates of the medication, relative to the date of first dose of study treatment.

Prior medications will be defined as any medication ended prior to the first dose of study treatment.

Concomitant medications will be defined as any medication started on or after the start of study treatment or any medication taken prior to the start of study treatment and continued after the start of study treatment.

- Vital signs:
The following vital signs parameters will be monitored: blood pressure, heart rate, respiratory rate, body temperature).

- Electrocardiogram (ECG):
The following ECG parameters will be recorded: HR, PR interval, QRS and QT.

- Laboratory Assessments:
Laboratory assessments will be performed for the following: Hematology, Toxicology (reactive protein), Biochemistry, Coagulation, Serology and Urine sampling. Appendix 9.3 provides a list of that laboratory test parameters that will be recorded.

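### Protocol 4.9.2 drops the V1B examination that other sections require, and the SAP has no Part B baseline, so delayed-start safety changes are measured from before Part A placebo

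*Protocol*

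**What the plan says.** **Examination at V1B.** Protocol section 4.9.2, on data to be recorded at Part B vaccination visits, has "Physical and neurological examination (except at V1B". Three other places in the protocol include V1B:

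- The synopsis account of Part B places the examination "at all face to face visits (V1B, V3B, V4B, V6B" and onward.
- The synopsis entry for the medical evaluation, whose first item is the physical and neurological examination, reads "To be performed at all visits, except telephone interviews".
- Section 8.2.4 gives its visit list as "V23 and V25 [Part A] and V1B, V3B, V4B, V6B" and onward. It adds that after V1 "any new finding or worsening of a previous finding from physical and neurological examination will be recorded" as an adverse event.

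SAP section 4.1.2 says "Neurological examinations are performed at all face-to-face visits", and the same of physical examinations, without naming V1B.

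**Safety bloods at V1B.** Section 4.9.2 has "Laboratory tests (hemogram, biochemistry and biological; at V1B: only biological", and section 8.2.2 starts Part B safety bloods at V3B ("Part A] and at visits V3B, V6B, V9B, V12B, V15B"). Two synopsis lists that cover safety and immune-response blood together do include V1B.

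**Reference for change.** SAP section 3 defines baseline, unless otherwise specified, as the last non-missing value before the first dose of study treatment. SAP sections 7.3.2, 7.3.3 and 7.3.7 report examination shifts, laboratory change and laboratory shifts from baseline by treatment sequence for Parts A and B, and specify no other reference. The Part B Day 1 in SAP section 3 serves study-day numbering only. For the antibody endpoint, protocol section 7.1.2.1 uses V1B as the pre-treatment visit for the delayed-start group.

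**The concern.** Protocol section 3.2.1 makes the safety of ABvac40 after delayed start an objective of Part B. For patients on placebo in Part A, V1B is the last moment before exposure. A site following section 4.9.2 would record no examination there; a site following section 8.2.4 would perform one.

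The baseline definition matters more for the analysis, and the error can run either way:

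- A value normal before Part A that became abnormal on placebo is shown at V3B as a shift in a table covering ABvac40 exposure.
- A value abnormal before Part A, normal at V23 or V25, and abnormal again after ABvac40 is shown at V3B as unchanged.

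There is also an effect on adverse events. A silent examination finding, or a laboratory abnormality judged clinically significant, that arises before V1B but is first seen at V3B becomes an adverse event. If its onset is dated to V3B, SAP section 7.2.1 assigns it to ABvac40.

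**Working it through.** The plan gives no figure to reproduce. The check compares the texts and counts days.

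**Texts on the V1B examination**

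| Place | V1B examination |
|---|---|
| Protocol 4.9.2 | excluded |
| Synopsis, Part B phases | V1B named |
| Synopsis, medical evaluation | every visit except telephone visits |
| Protocol 8.2.4 | V1B named |
| SAP 4.1.2 | face-to-face visits; V1B not named |

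The first row cannot be reconciled with the next three. The schedule tables are broken in the extracted text and were not used.

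**Inputs for the day counts**

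- V23 is day 539 and V25 day 728 of Part A; V3B is day 14 and V22B day 539 of Part B (study schemes).
- V1B follows completion of V23. Participation lasts 36 to 42 months in all and Part B lasts 18, so V1B falls at 36 − 18 = 18 to 42 − 18 = 24 months.
- Simplification: planned days, V1B between V23 and V25, no visit windows and no further gap.

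**Results for the delayed-start group**

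- Age of the SAP baseline at the first ABvac40 dose: about 539 to 728 days.
- Span of change at V3B from that baseline: 539 + 14 = 553 to 728 + 14 = 742 days. Share after ABvac40: 14/553 = 2.5% to 14/742 = 1.9%.
- Age of the baseline at V22B: 539 + 539 = 1,078 to 728 + 539 = 1,267 days.
- Age at V1B of the last V23 or V25 value: 0 to 728 − 539 = 189 days. Span of change at V3B from that value: 14 to 189 + 14 = 203 days. From a V1B value it is 14 days.

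**Weight of one patient**

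- Protocol section 9.2 expects at least 70 completers, 35 per group. Planned enrolment is 60 per group.
- Within the delayed-start group: 1/35 = 2.9%, or 1/60 = 1.7% at the enrolment ceiling.
- In the SAP's pooled ABvac40 adverse-event denominator: 1/(60 + 35) = 1/95 = 1.1%, or 1/(60 + 60) = 1/120 = 0.8%.
- The documents give no frequency for silent changes. If 1% to 5% of 35 patients had one (assumption), that is 0.35 to 1.75 patients, or 0.4 to 1.8 percentage points of 95.

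**The case against.** The strongest reply is that the data for a proper comparison are already on display. Late Part A visits appear in the by-visit laboratory summaries and examination shift tables, and listings run by patient, parameter and time. A value that turned abnormal on placebo and was present at V23 shows there as a shift. Clinically significant laboratory values and new examination findings at V23 or V25 are already adverse events. All this stands, and it limits the harm. It does not supply the within-patient change across the start of ABvac40. Subtracting one visit mean from another gives that change only if the same patients contribute, and gives no standard deviation. Two shift tables against an older baseline do not yield the cross-tabulation of V23 or V25 against V3B.

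A second reply is that section 4.9 governs what is recorded, while section 8.2.4 governs what is done. Even so, an unrecorded examination cannot serve as a reference. The thorough examination two hours after injection comes too late for that purpose.

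A reader might infer more than the documents support:

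- *That the SAP offers no reference before ABvac40.* It does: the Part A baseline precedes all treatment and V23 and V25 are tabulated. What is missing is a Part B baseline.
- *That section 8.2.4 requires the examination before injection.* It lists visits and gives no order. Section 4.9.1.2 lists it ahead of vaccination on the second day of V1, which supports that order for V1B.
- *That SAP section 4.1.2 plainly requires a V1B examination.* The protocol sometimes uses face-to-face for a type of safety visit distinct from vaccination visits (sections 4.2.2 and 4.9.2), and sometimes for all in-person visits (section 8.2.4).
- *That safety bloods at V1B were clearly intended, or clearly not.* Sections 4.9.2 and 8.2.2 omit them while the synopsis lists include V1B. This point does not depend on the answer.

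**Conclusion.** The point holds as a minor one, in two parts. The protocol contradicts itself on the V1B examination. The SAP defines no Part B baseline, so the delayed-start group's Part B laboratory changes and laboratory and examination shifts are measured from a value taken before placebo, about 539 to 728 days before the first ABvac40 dose.

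The effect is on the reading of descriptive safety data only. Part B tests no hypothesis (protocol section 4.1.2) and Part A analyses are untouched. V1B still has vital signs, weight, history and adverse-event review, and requires a supporting MRI result. The figure of 35 patients, and the pooled 95, are planning expectations and not upper bounds; on planned enrolment the ceilings are 60 and 120. The day counts assume planned visit days and entry to Part B at 18 to 24 months. How often a silent change would be misplaced is unknown.

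**What to change.** **Protocol.** Remove the V1B exception from the examination item in section 4.9.2, and state there or in section 8.2.4 that the V1B examination precedes the injection. The cost is a brief examination at an existing visit. Adding safety blood tubes to the V1B draw is optional.

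**SAP.** For the sequence with placebo in Part A and ABvac40 in Part B, add laboratory change and laboratory and examination shifts from the last value before the first ABvac40 dose. Use V1B if available, otherwise V23 or V25 with its age in days reported. Place these beside the summaries from the Part A baseline. The cost is one extra set of descriptive summaries; nothing is removed.

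**Study report.** State how many delayed-start patients were examined at V1B before injection.

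**Timing.** On the planned dates the last V1B falls about November 2020 (May 2022 minus 18 months) or March 2021 (September 2019 plus 18 months). Both follow the July 2020 protocol signatures and precede SAP version 1.0 of 25 November 2021. By the SAP stage, the practical remedy is probably the added summaries, which need only data already collected.

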4.9.3 Premature discontinuation visit (PDV)

In the event that a patient prematurely discontinues completely the study for any reason, a final assessment of the clinical trial (premature discontinuation visit) must be carried out as soon as possible after discontinuing the study, indicating the reason for discontinuation.

All patient documents should be as complete as possible.

For patients who prematurely discontinue the clinical trial the same assessments as the 50-weeks visit (V21, see 4.9.1) should be performed. However, if a randomized patient withdraws the study before receiving the first IMP administration the following assessments will not be needed: electrocardiogram; urine analysis (test strip); hemogram, biochemistry, biological activity, MRI, a-PET, CSF.

If a patient discontinues early from the study treatment, he/she should continue with the remaining safety assessment visits (without any more treatment administration nor related phone interviews) (see 5.3.4 for more details).

4.9.4 Information collected on selection failures

Subjects who have signed informed consent but were not randomized for any reason shall be recorded in the selection record and complete V0 in the eCRF. No further information will be collected on these subjects.

5 SELECTION AND WITHDRAWAL OF SUBJECTS

Study Population:

The study population will consist of a representative group of patients of both sexes with a-MCI or vm-AD, who meet all the selection criteria and give their informed consent to collaborate in the study, after being informed. The a-MCI will meet the clinical criteria defined by the National Institute on Aging–Alzheimer’s Association. The vm-AD will meet the criteria for probable AD defined by National Institute of Neurological and Communicative Diseases and Stroke/Alzheimer’s Disease and Related Disorders Association (NINCDS-ADRDA).

The patients’ recruitment will be competitive until the required number of patients is completed. Approximately 22 international centres will be involved: Spain (17 sites), France (3 sites), Sweden (1 site) and Italy (1 site).

5.1 Inclusion Criteria

A subject must meet all the following inclusion criteria:

1. Male or female between 55 and 80 years of age, both inclusive, at the time of signing informed consent.
2. The patient (or legal representative, if applicable) and a close relative/caregiver must read the subject information sheet, agree to participate in the clinical trial and sign the informed consent form (the patient and a close relative/caregiver).
3. Presence of a stable caregiver to attend the patient study visits.
4. Mini-Mental Status Examination (MMSE) score between 24 and 30 points (inclusive), according to age and education level.
5. Clinical Dementia Rating (CDR) scale scoring 0.5.
6. Repeatable Battery for the Assessment of Neuropsychological Status (RBANS) Score on the Delayed Memory Index (DMI) of 85 or lower.
7. The results of the patient’s MRI brain scan must be concordant with the diagnosis of clinical a-MCI or vm-AD according to the following criteria: Scheltens scale, and measurement of white matter and past haemorrhages.
8. If the patient is receiving treatment for AD, must have been stable during the two months before the selection visit.
9. Treatment for concomitant diseases must be stable during the previous month before the treatment of the study.
10. Positive assessment of the candidate by the investigator for complying with the requirements and procedures of the study.

5.2 Exclusion Criteria:

A subject meeting any of the following exclusion criteria is NOT eligible for participation in the study.

1. Known allergy to components of the vaccine or prior history of anaphylaxis, a severe allergic reaction or a history of hypersensitivity to any component of the formulation. Allergy to fish or shellfish.
2. Active infectious disease (i.e. hepatitis B, C). Positive syphilis serology.
3. History or presence of autoimmune disease, except mild eczema, rhinitis or psoriasis.
4. Presence or history of immunodeficiency (i.e. HIV).
5. Significant kidney and/or liver disease, as defined by plasma creatinine ≥ 2.5 mg/dL (221 $\mu\text{mol/l}$) and/or total bilirubin > 3 mg/dL (51.3 $\mu\text{mol/l}$) measured at the local site laboratory.
6. History of asthma or reactive airway disease with bronchospasm in the last 6 months, or currently on regular treatment.
7. Major uncontrolled systemic condition (e.g. diabetes, congestive heart failure, hypertension).
8. History of cancer (≤ 5 years since the last specific treatment). Exceptions: basocellular carcinoma.
9. Significant alterations in hematological, biochemical or urine analytical parameters, particularly those relating to levels of vitamin B12, folic acid or thyroid tests.
10. History of any other central nervous system disorder, degenerative or non-degenerative neurological or psychiatric condition that, in the investigator's opinion could be the cause of the dementia, or could explain the cognitive impairment, or that might interfere with cognitive function directly or by its treatment.
11. Geriatric Depression Scale (GDS; abbreviated version), score >5 .
12. Has a "yes" answer to C-SSRS suicidal ideation items 4 or 5, or any suicidal behavior within 6 months before Screening, or has been hospitalized or treated for suicidal behavior in the past 5 years before Screening.
13. History or signs of cerebrovascular disease (ischemic or haemorrhagic stroke, transient ischemic attack), or diagnosis of possible, probable or clear vascular dementia according to NINDS-AIREN criteria.
14. Presence on MRI of a relevant pattern of microvascular disease (Leukoaraiosis, Fazekas score ≥ 2 in the deep white matter scale or ≥ 4 in the global score) or more than one lacunar or territorial infarcts. Any other MRI finding that, in the opinion of the investigator, might be a relevant contributing cause of subject's cognitive impairment. Presence of up to 3 microhemorrhages will be acceptable.
15. History of bleeding disorder or predisposing conditions, blood clotting or clinically significant abnormal results on coagulation profile at Screening, as determined by the Investigator.
16. Patients being treated with anticoagulants or antiaggregant therapy (aspirin at a prophylactic dose ≤ 325 mg daily or clopidogrel at a dose ≤ 75 mg daily are allowed) should not be recruited in the study.
17. Modified Hachinski Ischemic Scale, score higher than 4.

18. Surgery (with general anaesthetic) within the previous three months to be included in the trial, or programmed during the study period.
19. Treatment within 30 days prior to visit 0 with systemic corticosteroids or other immunosuppressant's.
20. Vaccination against influenza or any other vaccination within 2 months before first IMP dose.
21. Patients, who have previously been randomized in this trial.
22. Participation in another clinical trial within the previous 1 month to screening visit, or within the previous 12 months after the last dose to the screening visit in the case of subjects who participated in trials with a study drug whose intention was to modify the progression AD unless documentation of receipt of placebo is available. The patient cannot be included in the study if the experimental drug was an immunotherapeutic drug, including IVIG or a vaccine against Alzheimer's disease unless documentation of receipt of placebo is available.
23. Patients with alcohol or drug abuse or dependence.
24. Absolute (having a pacemaker or implantable defibrillator) or relative (bare metal stent or stent implanted in the last six months) contraindications to MRI examination. Feeling of claustrophobic do not let perform MRI or PET scan.
25. Patients unlikely to comply with the protocol (e.g., unable to return for follow-up visits)
26. Women of childbearing potential, pregnant or nursing.
Note: All women will be considered to be of childbearing potential unless they are postmenopausal (amenorrheic for at least 12 consecutive months, in the appropriate age group, and without other known or suspected cause) or have been sterilized surgically (i.e. bilateral tubal ligation, total hysterectomy, or bilateral oophorectomy, all with surgery at least 1 month before dosing)
27. Significant alterations in the EKG that are associated with an added risk for the patient

